4. GENERAL STATISTICAL METHODS AND CONVENTIONS

4.1. General Methods

Summary statistics will be presented by treatment group, unless stated otherwise. Treatment group refers to patients receiving eteplirsen and patients in the untreated group.

For continuous variables, descriptive statistics will include the number of patients with data to be summarized (n), mean, standard deviation, median, minimum, and maximum.

For categorical/qualitative variables, descriptive statistics will include frequency counts and percentages. The total number of patients in a treatment group will be used as the denominator for percentage calculations, unless stated otherwise.

4.2. Handling of Missing Data

4.2.1 Imputation of Missing Values

CCI [REDACTED]

[REDACTED]

[REDACTED]

[REDACTED]

[REDACTED]

4.2.2 Handling of Incomplete Dates

All available data will be included in data listings and tabulations.

An incomplete date will occur when the exact date an event occurred or ended cannot be obtained for a patient. Incomplete dates will be imputed as described below. No other imputation of missing data will be performed.

- For a partial or missing medication date, the medication will be classified as a concomitant medication unless the available part of the date indicates it is impossible for the drug to be concomitant. For example, if only the year for the

stop date is available and the year is prior to the year of dosing, the medication will be classified as a prior medication.

- For a partial AE onset date, the event will be classified as treatment emergent if the month and/or year of the onset date are on or after the initiation of eteplirsen for eteplirsen treated patients or after Day 1 for untreated patients and within 28 days of the last dose of eteplirsen for eteplirsen treated patients or within a day after last visit for untreated patients, or if the month and/or year of the onset date are on or after the date of the qualifying visit for untreated patients. All AEs with a missing AE onset date will be classified as treatment emergent.
- For the purpose of calculating the time since DMD diagnosis or duration of prior corticosteroid use, if the date of DMD diagnosis or the start date of corticosteroid use has a missing day but known month and year, then the 15th of the month will be used in the calculation. If the date has a missing day and month and only the year is known, December 31st of the recorded year will be used in the calculation.

In all cases, the original missing or incomplete dates will be presented in the data listings.

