12. ADVERSE EVENTS

12.1. Collection of Adverse Events

Over the entire duration of the study, site personnel will ensure that all AEs are recorded appropriately. If an AE occurs, the primary concern is for patient safety, and the Investigator will use their judgment and expertise to determine the appropriate course of action.

All AEs from the time of informed consent through the End of Study visit (or early termination from the study) will be recorded in each individual patient's CRF. For eteplirsen-treated patients who prematurely discontinue the study (see [Section 9.5](#)), AEs will continue to be recorded until 4 weeks after the last eteplirsen infusion.

If, at any time after the patient has completed participation in the study (see [Section 9.5](#)), the Investigator or study staff becomes aware of an SAE that the Investigator believes is possibly/probably or definitely related to the IP ([Section 12.3.1](#)) or is possibly/probably or definitely related to a study procedure ([Section 12.3.2](#)), then the event and any known details must be reported promptly to the Sponsor.

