3.1.1 Randomization of Muscle Biopsy Schedule

All eteplirsen-treated patients will have a muscle biopsy performed at Baseline. Additionally, eteplirsen-treated patients will be randomly assigned 1:1 through interactive response technology (IRT) to a second muscle biopsy to be performed at Week 48 or 96. Untreated patients will not have muscle biopsies performed.

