For treated patients, an AE will be considered treatment-emergent if it starts in the time period starting with the initiation of the first dose of eteplirsen and ending 28 days after the last dose of eteplirsen. For untreated patients, an AE will be considered treatment-emergent if it starts on or after the Day 1 date.

Treatment-related Adverse Event

A treatment-related AE is any AE reported on the ADVERSE EVENTS eCRF that is marked as definitely related, or probably/possibly related to study drug.

Treatment Emergent Laboratory Abnormality

CCI [REDACTED]

[REDACTED]

[REDACTED]

[REDACTED]

[REDACTED]

[REDACTED]

[REDACTED]

[REDACTED]

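### SAP 4.2.2 makes an AE with a missing or partial onset date treatment-emergent even when its recorded stop date is before the first dose (or Day 1)

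*SAP*

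**What the plan says.** SAP 4.2.2 has two rules for AEs with incomplete onset dates.

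- **Onset wholly missing:** "All AEs with a missing AE onset date will be classified as treatment emergent".
- **Onset partly known:** the event is treatment-emergent if the month and/or year of onset fits the on-treatment period (treated) or the period from Day 1 or the qualifying visit (untreated). Only the onset date is tested.

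The same section adds "No other imputation of missing data will be performed", and no other visible section brings in the AE stop date.

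SAP 4.8 defines the term by onset. In the eteplirsen group the wording is "an AE will be considered treatment-emergent if it starts in the time period starting with the initiation of the first dose of eteplirsen"; the window closes 28 days after the last dose. For untreated patients the event must start on or after Day 1.

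The medication rule in SAP 4.2.2 works differently. A drug with an incomplete date is treated as concomitant "unless the available part of the date indicates it is impossible for the drug to be concomitant", and the SAP's own example of that exception is a stop date.

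**The concern.** AEs are collected before exposure begins. Protocol 12.1 says "All AEs from the time of informed consent through the End of Study visit (or early termination from the study) will be recorded", and SAP 3.1 allows a Screening/Baseline period of up to 5 weeks. Treated boys also have a procedure in that period: "All eteplirsen-treated patients will have a muscle biopsy performed at Baseline". Untreated boys have no biopsy, but their Screening/Week 1 assessments may also be spread over 5 weeks (Protocol 3). In either group an AE can therefore begin and end before Day 1.

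If the onset date of such an event is missing or partial, SAP 4.2.2 can put it in the TEAE tables although the stop date on record proves that it was over before exposure. Safety is the primary objective. Under SAP 5.8.1 it is in general only TEAEs that are tabulated, and other AEs are only listed, so the classification decides whether the event appears in the main safety tables.

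**Working it through.** The documents give no figure to reproduce. The check is to apply both rules to test events, then to bound the effect.

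**Step 1. Classification.** Day 1 is the first dose and days before it are negative. The exception tested is: not treatment-emergent if the stop date is before Day 1.

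| Onset | Stop | SAP 4.2.2/4.8 as written | With stop-date exception |
|---|---|---|---|
| Day -10 | Day -5 | Not TEAE | Not TEAE |
| Missing | Day -5 | **TEAE** | **Not TEAE** |
| Missing | Day +20 | TEAE | TEAE |
| Missing | Missing | TEAE | TEAE |

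Only the second event changes. Its onset can be no later than its stop, so onset is on or before Day -5, and SAP 4.8 gives not treatment-emergent. SAP 4.2.2 gives the opposite answer for the same record. The first row shows that a complete pre-dose onset date is handled correctly.

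**Step 2. Partial onset.** Suppose the onset is known only to the calendar month of first dose and the stop date is Day -5 in that month. A month can be compared only with the month of first dose, so the test is met and the event is a TEAE, although it ended before dosing. The same happens when only the year is known and it is the year of first dose.

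**Step 3. Largest effect on one preferred term.** Inputs: about 20 treated patients planned (SAP 3.3), 7 untreated patients enrolled (SAP 6.1), and each patient counted once per preferred term (SAP 5.8.1).

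- Treated: 1/20 = 5.0 percentage points per affected patient (2/20 = 10.0; 3/20 = 15.0).
- Untreated: 1/7 = 14.3 percentage points per affected patient.

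These are maxima. If the patient has another TEAE of the same term, the term's incidence does not change. Counts of events, which SAP 5.8.1 also tabulates, rise by one for each misclassified event in either case.

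**Step 4. How often.** The documents give no rate, so p, the chance that a treated patient has such an event, is assumed. The expected number of affected patients is 20p, and P(at least one) = 1 - (1 - p)^20.

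| Assumed p | Expected patients | P(at least one) |
|---|---|---|
| 0% | 0 | 0 |
| 1% | 0.2 | 0.18 |
| 2% | 0.4 | 0.33 |
| 5% | 1.0 | 0.64 |

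**The case against.** The strongest reply is that this is a deliberate conservative default for dates that should seldom be missing. Protocol 12.4 requires the date and time of both onset and resolution. Protocol 13.1 plans full source data verification, and Protocol 13.2 has missing data queried. A biopsy complication with a recorded end but no onset day, month or year is hard to picture. Under Protocol 2, footnote a, the Baseline visit may fall on the Week 1 day where the infusion site is also the surgical unit, which shortens or removes the interval between biopsy and dosing. The rule cannot hide a signal, and SAP 4.2.2 keeps the original incomplete dates in the listings. All of this stands, and it keeps the severity low. It does not rescue the rule: conservatism justifies assuming emergence when timing is unknown, and here the stop date settles the timing.

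It can also be said that the medication rule is no fair comparison, because a stop date bears directly on concomitant use while TEAE status depends on onset. That is partly right: the two bullets do not contradict each other. The conflict is between the AE rules in 4.2.2 and the definition in 4.8. The medication bullet shows only that the SAP already accepts the principle of not overriding a date that rules a classification out.

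Three stronger readings are tempting, and the documents do not support them:

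- **A reader might infer that pre-dose biopsy events in general become eteplirsen TEAEs.** They do not. With a complete onset date before first dose they are non-emergent under SAP 4.8.
- **A reader might infer that each misclassified event adds 5 points.** It adds at most that, because of the once-per-term count. Treated boys are also scheduled for a second, on-treatment biopsy, so the same procedural term may already be counted.
- **A reader might infer a biased comparison, since only treated boys are biopsied.** SAP 6.1 rules out any direct comparison or inferential statistic between the groups. Any distortion is to each group's own reported incidence.

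**Conclusion.** The two AE rules in SAP 4.2.2 are wrong as written for one narrow class of record: onset missing, or known only to the month or year of first dose (for untreated patients, of Day 1), with a stop date showing that the event ended before first dose or Day 1. For those records they contradict SAP 4.8.

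The bound of about 5 points (treated) or 14 points (untreated) per affected patient assumes that about 20 and 7 patients are in the analysis set and that the patient has no other TEAE of that term. The frequency is unknown, and the rates in the working are assumptions. The Protocol's data-quality provisions suggest few such events or none. The direction is always towards more TEAEs. Severity is low; the reason to act is that the misclassification is provable from data already collected.

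**What to change.** Add the following to both AE rules in SAP 4.2.2 (missing onset and partial onset):

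*unless the available part of the AE stop date shows that the event ended before the first dose of eteplirsen (treated) or before Day 1 (untreated), in which case it is not treatment-emergent.*

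Keep the present default for everything else. An event with no stop date, a stop date on or after Day 1, or a partial stop date that does not settle the matter stays treatment-emergent.

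The cost is one sentence in the SAP and one condition in the AE dataset program, to be made before database lock. The stop date is already required on the CRF, so no new data are needed.

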9.2. Patient Inclusion Criteria

A patient must meet all of the following criteria to be eligible for this study.

1. Be a male with DMD and meet one of the following criteria:
 - Have an out-of-frame deletion amenable to exon 51 skipping (eg, deletions of exons 45-50, 47-50, 48-50, 49-50, 50, 52, 52-63) as documented by a genetic report from an accredited laboratory confirming deletion endpoints by multiplex ligation-dependent probe amplification (MLPA) or sequencing. These patients will be enrolled into the eteplirsen-treated group.
 - Have a deletion mutation that is not amenable to correction by exon 51 skipping as documented by a genetic report from an accredited laboratory confirming deletion endpoints by multiplex ligation-dependent probe amplification (MLPA) or sequencing. These patients will be enrolled into the untreated group.
2. Be 4 to 6 years of age, inclusive, at the Screening visit.
3. Has been on a stable dose of oral corticosteroids for at least 12 weeks prior to study drug administration *and* the dose is expected to remain constant (except for modifications to accommodate changes in weight) for at least the first 12 weeks of the study OR has not received corticosteroids for at least 12 weeks prior to study drug administration and does not expect to start corticosteroids within the first 12 weeks of eteplirsen dosing.
4. Have intact right and left biceps muscles or 2 alternative upper arm muscle groups.
5. Have a parent(s) or legal guardian(s) who is able to understand and comply with all the study requirements.
6. Have a parent(s) or legal guardian(s) who is willing to provide written informed consent for the patient to participate in the study.

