5.2. Demographics and Baseline Characteristics

Demographic characteristics including age (years), race, ethnicity, and baseline characteristics including height (cm), weight (kg), body mass index (BMI; kg/m²), time since DMD diagnosis (months) to Baseline, corticosteroid type (Deflazacort or Prednisone), corticosteroid frequency (continuous versus intermittent), mutation type(s), and duration of prior corticosteroid treatment (months) to Day 1 will be summarized by treatment group. Demographic data and baseline characteristics will also be presented in data listings.

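### Setting year-only diagnosis and steroid start dates to December 31 can only shorten the baseline durations, and gives negative values when the recorded year is the year of Baseline or Day 1 (minor)

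*SAP*

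**What the plan says.** SAP 4.2.2 has a rule for incomplete dates that serves two derived baseline variables: "For the purpose of calculating the time since DMD diagnosis or duration of prior corticosteroid use". It has two branches.

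- Day missing, month and year known: "then the 15th of the month will be used in the calculation".
- Day and month missing: "only the year is known, December 31st of the recorded year will be used in the calculation".

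Apart from the date rules in that section, "No other imputation of missing data will be performed". The legible text neither limits the imputed date to the end of the interval nor explains the choice of December 31.

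SAP 5.2 summarises the two results by treatment group: "time since DMD diagnosis (months) to Baseline" and "duration of prior corticosteroid treatment (months) to Day 1". The intervals therefore end at different points, Baseline for the first and Day 1 for the second. SAP 4.8 defines Day 1 as the first eteplirsen administration for treated boys and the last Screening/Week 1 assessment for untreated boys. SAP 4.1 includes the minimum among the statistics reported for continuous variables.

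For boys on steroids at entry, Protocol 9.2 (inclusion criterion 3) sets a floor on prior use: "Has been on a stable dose of oral corticosteroids for at least 12 weeks prior to study drug administration".

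**The concern.** The two branches follow different logic. The 15th lies near the middle of the month, so its errors roughly cancel. December 31 is the latest date compatible with the record, so its errors all have the same sign and do not cancel however many boys are affected.

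The rule also ignores where the interval ends. A boy diagnosed, or started on steroids, in the calendar year of Baseline or Day 1 is given a date after that point, and his duration becomes negative. This is a realistic case for diagnosis: boys enter at age 4 to 6 (Protocol 9.2), and Protocol 6.1 puts the usual age at diagnosis at 3 to 5 years.

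At stake is the accuracy of two lines of the baseline table, in a trial whose title describes the disease as early-stage. A single such boy could put an impossible minimum in that table.

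**Working it through.** The plan gives no figure to reproduce, so this is calendar arithmetic. Months are days / 30.4375.

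**Inputs.** The imputation rules are from SAP 4.2.2 and the interval end points from SAP 5.2 and 4.8. The 12-week (84-day) floor is from Protocol 9.2. Group sizes are about 20 treated (SAP 3.3) and 7 untreated enrolled (SAP 6.1). *Assumption, not in the documents:* true dates are uniform over the recorded year.

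**1. Shortening per affected boy = December 31 − true date.**
- Range: 0 days (true date December 31) to 364 days (true date January 1), or 365 in a leap year; that is 0 to 12.0 months. This needs no assumption.
- Mean under uniformity: (0 + 364)/2 = 182 days; 182/30.4375 = 5.98 months (182.5 days, 6.00 months, in a leap year).
- Same calculation for the 15th-of-month rule: mean bias −0.7 day, range −16 to +14 days.

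**2. Recorded year equals the year of the end date.** Imputed duration = end date − December 31 of the same year. It is negative for 364 of 365 possible end dates and zero only on December 31. No distributional assumption is needed.

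| End date | Imputed duration |
|---|---|
| April 1 | −274 days = −9.0 months |
| July 1 | −183 days = −6.0 months |
| October 1 | −91 days = −3.0 months |

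Because time since diagnosis ends at Baseline, a boy with Baseline in December and Day 1 in January can also have a negative value when the recorded year is the Baseline year.

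**3. Conflict with the 12-week floor (boys on steroids at entry, non-leap year).**
- Start in the Day 1 year: this is compatible with inclusion criterion 3 only if Day 1 is January 1 + 84 days = March 26 or later. The imputed duration is then zero or negative, hence under 84 days.
- Start in the previous year: December 31 + 84 days = March 25. Any Day 1 before March 25 gives an imputed duration under 12 weeks.
- Worked case: Day 1 is July 1 and the true start is between January 1 and April 8. The true duration is 84 to 181 days (2.8 to 5.9 months), mean 132.5 days. The imputed duration is −183 days. Mean error is (132.5 + 183)/30.4375 = 10.4 months.

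**4. Effect on a group mean.** Each affected boy moves the mean by 5.98/n on average: 5.98/20 = 0.30 months (treated) and 5.98/7 = 0.85 months (untreated). Three affected boys among 20 move it by 3 × 0.30 = 0.90 months. The number affected is not given, so the average shift runs from 0 (none) to 5.98 months (all).

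**5. July 1 as the alternative.** Error over a 365-day year: mean −1 day (a very slight lengthening), range −183 to +181 days. Mean absolute error falls from 5.98 to 3.00 months. July 1 alone still gives a negative duration if the end date is in the recorded year and before July 1, so a bound at the end date is also needed.

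**The case against.** The strongest reply is that nothing in the visible analysis depends on these variables. SAP 4.5 has no covariate adjustment, SAP 4.6 has no subgroups, and SAP 6.1 rules out any inferential comparison of treated with untreated boys. The safety and dystrophin analyses do not use them in the legible text. This stands, and it sets the severity.

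It can also be said that the worst case may be rare and would be noticed. A site that confirms 12 weeks of stable steroid use will usually know the month of a recent start. Protocol 13.1 and 13.2 require full source verification and queries on missing data. The original incomplete dates are listed, and a negative minimum would show in the table. Rarity is plausible but cannot be checked from the documents. Visibility lets someone find the error but does not correct the summary.

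Three stronger readings may tempt a reader, and the documents do not support them.

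- *The cohort as a whole appears about 6 months earlier in disease.* Six months is a mean per affected boy under an assumed distribution, not a cohort shift. Age, which defines entry, is summarised separately and is untouched by the rule.
- *The rule distorts a comparison with natural-history data.* SAP 6.1 states that no external-control analysis will be performed under this plan. SAP 3.4.2 sends any later one to a possible separate SAP and a standalone report, and neither section says which variables it would use.
- *Eligible boys would be treated as ineligible.* Eligibility is confirmed by the site at Baseline and Week 1 (Protocol 2), and the imputation is stated only for calculating the two durations.

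SAP 4.2.1 and parts of 4.8 are blacked out, so a limit on imputed dates there cannot be fully excluded. The date rule itself is legible in full and contains none.

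**Conclusion.** The point holds as a minor defect. Two parts need no assumption: the December 31 rule never lengthens a duration, and it produces a negative one whenever the recorded year is the year of the end date, unless that date is December 31. The conflict with the 12-week floor is likewise a matter of dates, but it concerns only boys on steroids at entry. The mean of about 6 months rests on the uniform-date assumption; without it, all that can be said is 0 to 12 months per affected boy. The reach is limited to two descriptive lines in SAP 5.2, for an unstated number of boys, possibly none. No safety or dystrophin conclusion in the visible plan would change.

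**What to change.** Replace the year-only sentence in SAP 4.2.2 with a rule of this kind:

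1. Impute a year-only date to July 1 of the recorded year, in line with the mid-month rule beside it.
2. If July 1 falls after the end of the interval (Baseline for time since diagnosis, Day 1 for steroid duration), use the midpoint between January 1 of that year and the end date. No duration is then negative. For example, with Baseline on April 1 the midpoint lies 45 days (1.5 months) before Baseline, where the present rule gives −9.0 months.
3. For treated boys on steroids at entry, place the imputed start no later than 12 weeks before Day 1, provided this stays within the recorded year; otherwise query the date. In the July 1 worked case this gives a start of April 8 and a duration of 84 days. The mean error falls from 10.4 months to (132.5 − 84)/30.4375 = 1.6 months.

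Step 3 is limited to treated boys because the criterion counts back from study drug administration, which untreated boys do not have.

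The cost is a short rewording of one SAP rule and a small change in the derivation program. No new data are needed, beyond a query for any steroid start that step 3 cannot place.

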4.3. Analysis Populations

There will be 3 analysis populations with the definitions below for analyzing safety data, efficacy data, biopsy data and pharmacokinetics, as appropriate.

- **Full Set:** Full set includes all patients who are enrolled in the eteplirsen group and receive at least 1 dose of eteplirsen as well as all patients who are enrolled in the untreated group who have at least 1 assessment post-enrollment assessment. Full Set will be used for summarizing safety and efficacy data.
- **Muscle Biopsy Set:** This set includes all patients who receive at least one dose of eteplirsen and who have data from both Baseline (pre-treatment) and Week 48 or Week 96 (on-treatment) muscle biopsy samples.
- **Pharmacokinetic Set:** All patients who receive at least one dose of eteplirsen and for whom there are adequate PK samples with which to estimate PK parameters. The PK Set will be further described in a separate PK SAP.

